If your application involves the use of a HUD "humanitarian" device: describe whether the use is for "on-label" clinical patient care, "off-label" clinical patient care, and/or research (collecting safety and/or effectiveness data).

The purpose of this study is to explore the effectiveness of interventions that may be useful during aeromedical evacuation (AE) or prolonged filed care (PFC).

Skin cellular injury, skin perfusion, and skin microclimate will be tested with and without Mepilex sacral dressing or LiquiCell pads on 3 transport surfaces. Note: A litter is a stretcher.

Aeromedical Evacuation (AE) conditions

- Mepilex: Litter + AE mattress + 30° backrest
- Without Mepilex: Litter + AE mattress + 30° backrest
- Mepilex: Vacuum Spine Board (VSB) placed on AE mattress
- Without Mepilex: Vacuum Spine Board (VSB) placed on AE mattress

Prolonged Field Care (PFC) conditions

- LiquiCell: Talon Litter
- Without LiquiCell: Talon Litter

Aim 1. Under conditions simulating aeromedical evacuation (stretcher + mattress or stretcher + mattress + vacuum spine board) compare the effects of with/without Mepilex (multilayered dressing) on the buttocks/lower back (sacrum) on indicators of skin injury, skin blood flow and oxygenation, skin temperature and moisture and pressure between the support surface and the skin (interface pressure).

Aim 2. Under conditions simulating prolonged field care (field stretcher without a mattress pad) evaluate the effect of with/without LiquiCell (a pad with fluid-filled pocked of liquid) placed under the back and bottom on indictors of skin injury, blood flow, oxygenation, temperature, moisture and interface pressure.

(1.6) Study design. Provide a one-sentence description of the general study design and/or type of methodology.

Your answer will help HSD in assigning applications to reviewers and in managing workload. Examples: a longitudinal observational study; a double-blind, placebo-controlled randomized study; ethnographic interviews; web scraping from a convenience sample of blogs; medical record review; coordinating center for a multi-site study.

Stratified randomized control trial with subjects assigned to either the AE or Prolonged Field Care arms with or without the intervention. Stratification will be based on body fat percentage.

(1.7) Intent. Check all the descriptors that apply to your activity. You must place an "X" in at least one box.

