5 PROCEDURES

5.1 Study procedures. Using lay language, provide a complete description of the study procedures, including the sequence, intervention or manipulation (if any), drug dosing information (if any), use of records, time required, and setting/location. If it is available and you think it would be helpful to the IRB: Upload a study flow sheet or table to the **Supporting Documents** SmartForm in **Zipline**.

For studies comparing standards of care: It is important to accurately identify the research procedures. See UW IRB POLICY:
Risks of Harm from Standard Care and the draft guidance from the federal Office of Human Research Protections, "Guidance on Disclosing Reasonably Foreseeable Risks in Research Evaluating Standards of Care"; October 20, 2014.

Researcher Date & Version

The study will take place in a temperature-controlled room (~72°F) at the University of Washington School of Nursing. Subjects will be assigned to one of six groups. Each subject will be clothed in a single layer of cotton like clothing (scrubs) and undergarments and socks. Height and weight will be obtained using a standup calibrated device and body fat will be measured using the InBody 570 Body Composition Analyzer. This device is used for medical research and in health clubs and involves standing on a scale.

Group Assignment: Subjects will first be stratified based on body fat percentage (< 10%, 10%-20%; > 20%). Using close block stratification, subjects will be randomly assigned to one of six groups to ensure distribution based on body composition.

Aeromedical Evacuation (AE) conditions

- Group 1: Mepilex: Litter + AE mattress + 30° backrest
- Group 2: Without Mepilex: Litter + AE mattress + 30° backrest
- Group 3: Mepilex: Vacuum Spine Board (VSB) placed on AE mattress
- Group 4: Without Mepilex: Vacuum Spine Board (VSB) placed on AE mattress

Prolonged Field Care (PFC) conditions

- Group 5: LiquiCell: Talon Litter
- Group 6: Without LiquiCell: Talon Litter

All Groups

[figure not shown]
Acclimation: All subjects will complete a 20-minute acclimation period in the study room.

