Placement of Sensors: After completion of the height, weight and body fat measurements, the subject will lie down on the study surface and the temperature/oxygen sensors will be placed on the lower aspect of their back and one oxygen sensor placed on their chest (approximately 2 inches below the collar bone on the left chest). The transcutaneous oxygen (TcPO2) probes will heat up to 111°F, as recommended by the device manufacturer.

The subject will rest on their side for approximately 15 minutes while the measurements from the sensors to stabilize. These sensors allow for continuous measurement of skin tissue oxygenation and temperature.

Stabilization: Following acclimation, the subject will be assisted to a side lying position (unloaded) and the temperature and TcPO2 probes will be placed. Based on our previous research, it takes approximately 15 minutes for the sacral probe to stabilize ($TcPO_2 < \pm 2 \text{ mm Hg for 4 minutes}$).

Cytokine/Skin Moisture Measurements: After stabilization four small pieces of tape (Sebutape) will be placed on the lower back for 1 minute for the measurement of interleukin 1/Total protein. The Sebutape (size: 0.75 x 1.1 inches) will be placed in four quadrants (sacrum/buttocks). Sebutape has been used to measure IL- α in studies related to pressure and shear; including the evaluation of Mepilex under conditions of pressure and shear. Removal of the tape causes minimal stripping of the stratum corneum and discomfort to the subject. The Sebutape will be handled using blunt tweezers and gloved hands to avoid any cross contamination. Four patches will be applied (two on sacrum/two on buttocks) to intact, unblemished skin that is free of excessive hair, but which allows us to characterize potential injury on the buttocks and sacrum (areas of pressure injuries noted in Mok's study). After the one-minute sampling period the Sebutape will be removed using blunt tweezers and will be placed flat (avoid any crumpling or folding) into an individually labeled vial and immediately frozen on ice.

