Skin Moisture. We will also use a noninvasive probe to measure the amount of moisture in the skin on the lower back/sacrum. Two components of skin moisture will be measured: 1) Epidermal moisture, which reflects perspiration and 2) subepidermal moisture using a Delfin MoistureMeter D (Delfin Technologies, LTD, Grennwich, CT) dermal phase meter (http://www.delfintech.com/en/product_information/moisturemeterd/). Epidermal moisture (stratum corneum) will be measured at 0.5 mm below the skin surface and subepidermal moisture (i.e., below the epidermal stratum corneum layer) will be measured at a depth of 2.5 mm. The device consists of a control unit (signal producer) and a probe (open-ended coaxial transmission line), which is placed in contact with the skin The skin moisture will be measured at a standardized site, mid-sacrum, approximately 2 cm above the gluteal fold (avoiding the sites of the Sebutape). This location will be marked with ink pen to assure the same location for repeat measurement. For each depth, the probe will be placed on the skin surface and held for 5 seconds.

After these measurements are complete, subjects in the Mepilex dressing groups will have the dressing placed on their lower back/buttocks. All subjects will then complete an additional 5 minutes in the side-lying position, after which they will lie on their back on the designated surface. After positioning a sheet will be placed over the subject for comfort. A pillow may be placed under the head and heels at the subject's discretion.

The skin interface pressure will be measured continuously during the loaded period using the XSensor™ System (Crown Therapeutics, Belleville IL) with X3 Medical v6.0 software. This pad, which is similar to a sheet, will be positioned on the surface. *Peak skin-interface pressure*, which is the highest measured pressure for each body region and the *Peak Pressure Index* (PPI), which is the average of a 3 x 3 sensor area representing the highest pressure (including the peak pressure cell). The sacrum/buttocks will be divided into four quadrants based on the vertebral column and top of the gluteal cleft.⁵⁵ For the Mepilex groups, the pressure on the surface of the Mepilex will be recorded. Although this procedure does not directly measure skin interface pressure, which may be decreased by the Mepilex, it is not possible to place the pressure mat between the Mepilex and the skin.

Unique Procedures by Study Group

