## Cover

**Official Title of Study**: Prevention of Pressure Injuries During Aeromedical Evacuation or Prolonged Field Care

#NCT03924622

Date: 4 Jan 2019

Statistical Analysis Plan This study proposes to compare the effect of presence or absence of a Mepilex dressing) on variables (IL- $1\alpha$ /TP, TcPO2, interface pressure, skin temperature and moisture) potentially reflecting the modified effects of pressure, shear and microclimate associated with lying for an interval of (120 minutes) on either a standard NATO litter with mattress or a VSB. Primary analyses will contrast the Mepilex and non-Mepilex dressing groups, WITHIN the two support platform strata. That is, the two contrasts LITTER + Mattress (Mepilex vs. not) and VSB (Mepilex vs. not) will be the analysis foci. Analyses of the effect of support platform, and the interactions of platform with presence/absence of Mepilex pad will be considered secondary and exploratory. The statistical tests will be based on a group (Mepilex vs. non-Mepilex) by time (first sample – unloaded baseline, second sample post 120-minute loading) analysis. Analysis options depending on data structure include a repeated measures Group x Time ANOVA, an ANCOVA-based group analysis of the post-loading measurement controlled for the preloading measurement, a group analysis of the simple change score (post-loading – preloading), and a longitudinal analysis of the two-time points by group using Generalized Estimating Equations or a Linear Mixed Models. It is important to note that several of the studies using IL-1 $\alpha$  as a dependent variable have used non-parametric statistical tests. Similarly, error bar plots in published papers document a degree of heteroscedasticity, with the variability in a batch apparently having considerable dependence on its mean. This potential non-normality problem may be met with data transformation (e.g., square root or logarithmic transform) to an appropriate carrier or use of Generalized Linear Models with an appropriate non-linear monotonic link function, or the use of non-parametric statistics. As an example of application of the last method to the current data structures, the simple change score or residual change score from pre- to post- loading could be analyzed with the non-parametric Mann-Whitney U test. Power Analysis: The a priori justification of group sample size with respect to statistical power will be based on the potential change in the variable (IL- $1\alpha$ /Total ratio), which is measured in each participant immediately before and after lying for 120 minutes on the support platform. The analyses of other variables (e.g., TCPO2, interface pressure, skin temperature/moisture) will be treated as descriptive and secondary. When there is limited evidence in the literature that bear directly on the estimation of an effect size in planning a preliminary study, several authors and agencies have argued for setting the sample size per group N per group = 12.76-78 Assuming two tailed two independent group comparisons, with an adjusted significance threshold set to alpha = 0.025 to accommodate multiple testing at the alpha = 0.05 level for both the NATO litter and the "VSB" strata, and the size of each group N = 12, the minimum Cohen's d effect size per test necessary to achieve statistical power P = 0.80 is d = 1.336, which is considered a very large and ambitious effect size. However, there is related support in the literature that this level of effect is achievable using the proposed protocol. Hemmes55 (see Fig. 3, page 86, and Table A1, page 88) demonstrated that lying on either a rigid or soft-layered spineboard for 60 minutes raised mean sacral IL- $1\alpha$ /TP ratio by more than a factor of 10. de Wert24 (see Fig. 4A, page 510), using a 30- minute pressure and shear loading protocol on the forearm, showed that the presence of a Mepilex dressing resulted in IL-1 $\alpha$ /TP ratio levels that were on the order of 7 times smaller than the "no dressing" condition.

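### Minor, Groups 1 to 4: Mepilex or none is assigned before the baseline IL-1α/TP tapes but first acted on after them, and the protocol does not say when staff learn it

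*Protocol*

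**What the plan says.** Section 1.6 of the protocol gives the design as a "Stratified randomized control trial with subjects assigned to either the AE or Prolonged Field Care arms with or without the intervention". That sentence shows that with/without is part of the assignment; it says nothing about timing. The timing comes from section 5.1:

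- **Assignment.** After stratification on body fat: "Using close block stratification, subjects will be randomly assigned to one of six groups to ensure distribution based on body composition". Each of the six groups is a platform together with the presence or absence of Mepilex or LiquiCell.
- **Surface.** "After completion of the height, weight and body fat measurements, the subject will lie down on the study surface", so the platform must be known by then. About 15 minutes of probe stabilisation follow.
- **Baseline tapes.** "After stabilization four small pieces of tape (Sebutape) will be placed on the lower back for 1 minute". The sites are set by region and skin condition: "Four patches will be applied (two on sacrum/two on buttocks) to intact, unblemished skin that is free of excessive hair".
- **Baseline moisture.** This is read at a fixed mid-sacral site marked in ink.
- **Dressing.** "After these measurements are complete, subjects in the Mepilex dressing groups will have the dressing placed on their lower back/buttocks".

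The SAP sizes the study on the IL-1α/total protein ratio. Its primary contrasts are Mepilex against none within litter + mattress and within the vacuum spine board. It compares an unloaded baseline sample with a "second sample post 120-minute loading" and treats moisture and the other measures as descriptive and secondary.

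**The concern.** When the baseline tapes go on, staff need to know which surface the subject lies on. In Groups 1 to 4 they do not yet need to know whether a dressing will follow. The protocol nevertheless fixes both in a single step beforehand and is silent on when the second part is disclosed.

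The baseline tape sample is half of the endpoint on which the study is sized, and no listed analysis avoids it: Group × Time ANOVA, ANCOVA, change score, GEE or mixed model, and Mann-Whitney on change or residual change. If knowledge of the arm influenced where the tapes were placed or how they were handled, the resulting baseline difference would pass into the change score in full and into ANCOVA in part. This exposure arises only from the order of disclosure, so it can be removed without altering the design.

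**Working it through.** **The plan's own figure.** With 12 per group, two-sided alpha 0.025 and d = 1.336, the noncentrality is 1.336 × √(12/2) = 3.273 on 22 df, with critical value 2.405. Power is 0.79997, so the stated 0.80 reproduces. Nothing below changes it.

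**Sequence, Groups 1 to 4**

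| Step in section 5.1 | Platform needed? | Mepilex or none needed? |
|---|---|---|
| Subject lies on the study surface | yes | no |
| Probe stabilisation | yes | no |
| Baseline tapes | yes | no |
| Baseline moisture | yes | no |
| Dressing applied, or not | yes | **yes, first use** |

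The Mepilex assignment is therefore fixed earlier than it is used. Whether it is also known earlier is not stated.

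**What a shift would do.** The documents give neither a shift nor a correlation, so both are assumptions. Let δ be an arm-related shift in mean baseline, in SD units, with no true effect and equal pre and post SDs. Let ρ be the pre/post correlation.

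- Standardised bias in the change score: δ / √(2(1 − ρ)), 22 df.
- Standardised bias in ANCOVA: ρδ / √(1 − ρ²), 21 df.
- Test size: noncentral t with noncentrality bias × √6, two-sided 0.025.

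Example with ρ = 0.5 and δ = 0.5: the change-score bias is 0.5/√1 = 0.5, giving size 0.139. The ANCOVA bias is 0.25/√0.75 = 0.289, giving size 0.059.

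| ρ | δ | Change score | ANCOVA (formula) |
|---|---|---|---|
| 0.3 | 0.1 | 0.028 | 0.025 |
| 0.3 | 0.25 | 0.043 | 0.027 |
| 0.3 | 0.5 | 0.104 | 0.035 |
| 0.5 | 0.1 | 0.029 | 0.026 |
| 0.5 | 0.25 | 0.051 | 0.033 |
| 0.5 | 0.5 | 0.139 | 0.059 |
| 0.7 | 0.1 | 0.032 | 0.029 |
| 0.7 | 0.25 | 0.069 | 0.049 |
| 0.7 | 0.5 | 0.227 | 0.134 |

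The ANCOVA formula ignores the extra variance caused by the baseline imbalance. Simulation with an estimated slope puts the last ANCOVA cell at about 0.12, which is the figure to use. With δ = 0 every cell is 0.025. With two time points, the Group × Time interaction is the change-score test.

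**The case against.** The strongest objection is that nothing in the documents shows the tapes being taken with the arm known. They do not say when the sampling staff learn the Mepilex assignment. The answer on un-blinding in section 10.7 is cut off in the text available, and the grant application and monitoring plan are attachments not included here. A reader might infer an established unmasked baseline or an established bias. Neither is supported; the text shows only that disclosure timing is unspecified and no masking is described.

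The mechanism is also weak. The endpoint is a laboratory ratio, and dividing by total protein should damp differences in how much material each tape picks up. Tape size, one-minute contact, the four sites by region and handling with tweezers and gloves are all specified. What remains open is the exact spot and the handling, and the documents give no reason why that should move the baseline systematically by arm. This is why a 0.1 SD shift belongs in the range.

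Three wider readings should be set aside:

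- **Moisture.** The site is fixed and ink-marked and the measure is secondary. The point concerns the tapes.
- **LiquiCell.** Section 5.1 does not say whether the mat is already on the litter at baseline, so it is not established that only the platform is needed in Groups 5 and 6. These groups are also outside the SAP's primary contrasts.
- **Losses from a known arm before baseline.** Section 2.7 reports no discontinuations in the earlier study (40 minutes supine) and allows 12 extra subjects.

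Finally, the post-load sample cannot be masked from the staff who remove the dressing, and a shift there would enter both analyses in full. Protecting the baseline is therefore a partial measure.

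All of this stands, and it limits the severity. The sequence itself is unaffected.

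**Conclusion.** This is a cheap improvement of minor severity, limited to Groups 1 to 4; it is not a demonstrated flaw. The Mepilex assignment is made before the baseline tapes, is not needed until after them, and has no stated disclosure time. The baseline of the sizing endpoint may therefore be collected with the arm known.

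The size of any bias cannot be derived from the documents. Under the assumed 0.1 to 0.5 SD shift and correlation of 0.3 to 0.7, the nominal 0.025 test has size about 0.028 to 0.23 for change scores and about 0.025 to 0.12 for ANCOVA. At 0.1 SD the change-score size is only 0.028 to 0.032. The upper figures are conditional on the largest assumed shift and correlation and should not be read as an estimate of what will happen.

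**What to change.** In section 5.1, keep the single six-group list stratified by body fat, and state that it is released in two parts:

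1. The platform is released at assignment.
2. Mepilex or none is released only after the baseline tapes are in their vials and the baseline moisture has been read.

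Apply the same rule to Groups 5 and 6 only if the LiquiCell mat is placed after baseline; section 5.1 should say whether it is. If staff already learn the Mepilex assignment at that point, a sentence recording this is enough.

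The cost is a two-part envelope or its equivalent, and the dressing has to be fetched after the baseline samples. Group sizes, strata, alpha of 0.025 and d = 1.336 are unchanged. The plan should acknowledge that the post-load sample remains unmasked.

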2 PARTICIPANTS

2.1) Participants. Describe the general characteristics of the subject populations or groups, including age range, gender, health status, and any other relevant characteristics.

Up to 84 subjects (non-military) will be recruited at the University of Washington (goal 72 subjects 12/group). Subjects will be randomly assigned to one of the six study groups. Characteristics described below.

- 2.2 Inclusion and exclusion criteria.
 - a. Inclusion criteria. Describe the specific criteria you will use to decide who will be included in your study from among interested or potential subjects. Define any technical terms in lay language.

Men and women aged 18 to 55 who meet the physical standards for military personnel and weigh less than 250 pounds (maximum allowable weight on the litter). Subjects must be able to remain in the study position for the duration of the study.

- b. Exclusion criteria. Describe the specific criteria you will use to decide who will be excluded from your study from subjects who meet the inclusion criteria listed above. Define any technical terms in lay language.
 - 1) previous injuries to sacrum/buttocks with scarring, 2) history of pressure injuries, 3) cardiovascular disease, 4) neurological disease that would affect vascular response, 5) diabetes, 6) history of malignancy, 7) current skin condition (e.g., eczema or psoriasis) which may interfere with the skin cytokine levels, 8) current neck/back pain or history of chronic neck/back pain, 9) known vertebral/spinal cord disease/injury (scoliosis, kyphosis, or lordosis), 10) self-reported pregnancy or 11) concern about their ability to remain in the vacuum spine board for 120 minutes. All subjects will be asked to refrain from the use of nonsteroidal anti-inflammatory medications for seven days before the experiment, to abstain from sun bathing for 24-hours before the experiment, to abstain from ingesting caffeine or smoking for six hours before the experiment, to avoid eating for 2 hours before the study (to increase accuracy of body fat measurement) and to not use any skin care products on the day of testing. Subjects will be informed of these requirements at the time of screening.
- **2.3) Prisoners**. IRB approval is required in order to include prisoners in research, even when prisoners are not an intended target population.
 - a. Will you recruit or obtain data from individuals that you know to be prisoners?

For records reviews: if the records do not indicate prisoner status and prisoners are not a target population, select "No". See the **WORKSHEET: Prisoners** for the definition of "prisoner".

X I IVO	
Yes	→ If yes, answer the following questions (i – iv).
	i. Describe the type of prisoners, and which prisons/jails:
	ii. One concern about prisoner research is whether the effect of participation on prisoners' general living conditions, medical care, quality of food, amenities, and opportunity for earnings in prison will be so great that it will make it difficult for prisoners to adequately consider the research risks. What will you do to reduce the chances of this?

#2003

V No

ZIPLINE APPLICATION: IRB Protocol

·	edures will be fair to all eligible	sure that (a) your recruitment and subject selection e prisoners and (b) prison authorities or other prisoners will r require particular prisoners from participating.
Wasi enco decis	nington State: check the box be urage or facilitate the use of a sions, and (b) clearly inform ea	ers in federal facilities or in state/local facilities outside of elow to provide your assurance that you will (a) not prisoner's participation in the research to influence parole och prisoner in advance (for example, in a consent form) will have no effect on his or her parole.
	Confirmed	
b. Is your research like	ly to have subjects who becom	ne prisoners while participating in your study?
For example, a longitude point during the study.	dinal study of youth with drug pro	bblems is likely to have subjects who will be prisoners at some
No		
		er while participating in your study, will you continue the ction while the subject is a prisoner?
□ N	•	stion while the subject is a prisoner:
Y		ocedures and/or data collection you will continue with
	prisoner subjects	
for any of these population	RB approval is required for the	use of the subject populations listed here. Check the boxes include in your research. (In other words, being a part of
for any of these population the population is an inclu	RB approval is required for the ons that you will purposefully ision criterion for your study.)	
for any of these population the population is an inclu The WORKSHEETS describe	RB approval is required for the ons that you will purposefully ision criterion for your study.)	include in your research. (In other words, being a part of
for any of these population the population is an inclu The WORKSHEETS describe	RB approval is required for the ons that you will purposefully i sion criterion for your study.)	include in your research. (In other words, being a part of ot need to be completed and should not be submitted.
for any of these population the population is an incluing the WORKSHEETS describe	RB approval is required for the ons that you will purposefully is is sion criterion for your study.) the criteria for approval but do not pulation	ot need to be completed and should not be submitted. Worksheet
for any of these population the population is an inclusion. The WORKSHEETS describe Po Fetuses in utero	RB approval is required for the ons that you will purposefully ision criterion for your study.) the criteria for approval but do not pulation ain viability	include in your research. (In other words, being a part of ot need to be completed and should not be submitted. Worksheet WORKSHEET: Pregnant Women WORKSHEET: Neonates
for any of these population the population is an inclusion. The WORKSHEETS describe Po Fetuses in utero Neonates of uncertains	RB approval is required for the ons that you will purposefully is is in criterion for your study.) the criteria for approval but do not pulation	include in your research. (In other words, being a part of ot need to be completed and should not be submitted. Worksheet WORKSHEET: Pregnant Women WORKSHEET: Neonates
for any of these population the population is an incluing the worksheets describe Po Fetuses in utero Neonates of uncertain the worksheets of uncertain the worksheet of the worksheets of uncertain the worksheet of uncertain the worksheets of uncertain the worksheet of uncertain the worksheet of	RB approval is required for the ons that you will purposefully ision criterion for your study.) the criteria for approval but do not pulation ain viability	include in your research. (In other words, being a part of ot need to be completed and should not be submitted. Worksheet WORKSHEET: Pregnant Women WORKSHEET: Neonates WORKSHEET: Neonates
for any of these population the population is an inclu The WORKSHEETS describe Po Fetuses in utero Neonates of uncertain Non-viable neonate Pregnant women a. If you check any of the	RB approval is required for the ons that you will purposefully ision criterion for your study.) the criteria for approval but do not pulation ain viability	include in your research. (In other words, being a part of ot need to be completed and should not be submitted. Worksheet WORKSHEET: Pregnant Women WORKSHEET: Neonates WORKSHEET: Pregnant Women

ZIPLINE APPLICATION: IRB Protocol

2.5 Native Americans or non U.S. indigenous populations. Will you actively recruit from Native American or non-U.S. indigenous populations through a tribe, tribe-focused organization, or similar community-based organization?

Indigenous people are defined in international or national legislation as having a set of specific rights based on their historical ties to a particular territory and their cultural or historical distinctiveness from other populations that are often politically dominant.

Examples: a reservation school or health clinic; recruiting during a tribal community gathering

X	No	
	Yes	→ If yes, name the tribe, tribal-focused organization, or similar community based organization. The UW IRB expects that you will obtain tribal/indigenous approval before beginning your research.

2.6) Third party subjects. Will you collect private identifiable information about *other individuals* from your subjects? Common examples include: collecting medical history information or contact information about family members, friends, co-workers.

"Identifiable" means any direct or indirect identifier that, alone or in combination, would allow you or another member of your research team to readily identify the person. For example, suppose that you are studying immigration history. If you ask your subjects several questions about their grandparents but you do not obtain names or other information that would allow you to readily identify the grandparents, then you are not collecting private identifiable information about the grandparents.

→ If yes, these individuals are considered human subjects in your study. Describe them and what data you will collect about them.

2.7 Number of subjects. Can you predict or describe the maximum number of subjects (or subject units) you need to complete your study, for each subject group?

Subject units mean units within a group. For most research studies, a group will consist of individuals. However, the unit of interest in some research is not the individual. Examples:

- Dyads such as caregiver-and-Alzheimer's patient, or parent and child
- Families
- Other units, such as student-parent-teacher

Subject group means categories of subjects that are meaningful for your research. Some research has only one subject group – for example, all UW students taking Introductory Psychology. Some common ways in which subjects are grouped include:

- By intervention for example, an intervention group and a control group.
- By subject population or setting for example, urban versus rural families
- By age for example, children who are 6, 10, or 14 years old.

The IRB reviews the number of subjects you plan to study in the context of risks and benefits. You may submit a Modification to increase this number at any time after you receive IRB approval. If the IRB determines that your research involves no more than minimal risk: you may exceed the approved number and it will not be considered non-compliance. If your research involves more than minimal risk: exceeding the approved number will be considered non-compliance.

No → If no, provide your rationale in the box below. Also, provide any information you can about the scope/size of the research. You do not need to complete the table.

Example: you may not be able to predict the number of subjects who will complete an online survey advertised through Craigslist, but you can state that you will post your survey for two weeks and the number who respond is the number who will be in your study.

Our goal is 12 subjects/group (N = 72). At the direction of the funding agency, we have added 12 additional subjects to account for any possible attrition. (Total recruitment = up to 84). Note: In our previous study, which used similar methods with subjects in supine position for 40 minutes, we did not have any subjects discontinue their participation.

x Yes

→ If yes, for each subject group, use the table below to provide your estimate of the maximum desired number of individuals (or other subject unit, such as families) who will complete the research.

Group name/description	Maximum desired number of individuals (or other subject unit, such as families) who will complete the research *For clinical trials: provide numbers for your site and for the study-wide total number
Group 1: Litter + mattress (no Mepilex)	12
Group 2: Litter + mattress (with Mepilex)	12
Group 3: Litter + mattress + vacuum spine board (with Mepilex)	12
Group 4: Litter + mattress + vacuum spine board (no Mepilex)	12
Group 5: Talon litter + LiquiCell	12
Group 6: Talon litter – no LiquiCell	12

